2.2 Study Endpoints

Product use endpoints are:

- Cigarettes smoked per day (CPD). Both compliant and non-compliant smoking should be captured in the e-diaries. For a definition of non-compliant smoking, see [Section 5.12.7.1](#).
- Number of collected used cigarette butts (apparent compliant, apparent non-compliant, and total).
- Puffing topography parameters (puff duration, puff volume, peak puff flow rate, average flow rate and inter-puff interval).

Nicotine PK endpoints are:

- C_{max}
- T_{max}
- AUC

BoE endpoints are:

- In urine
 - Total NNAL (NNK biomarker)
 - Total NNN
 - 3-HPMA (acrolein biomarker)
 - S-PMA (benzene biomarker)

- 1-OHP (hydroxypyrene biomarker)
- Total nicotine equivalents (T_{neq})
- Creatinine concentration (for normalization of urinary BoE endpoints)
- Carboxyhemoglobin in blood
- Cotinine in plasma

Subjective effects endpoints are:

- Fagerström Test for Cigarette Dependence (FTCD)
- Brief Questionnaire of Smoking Urges (QSU-Brief)
- Minnesota Nicotine Withdrawal Scale - Revised (MNWS-R)
- Perceived health risk scale

Safety endpoints include:

- Adverse events (AEs)

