1.3 Hypothesis

It is anticipated that when adult smokers switch to smoking VLN cigarettes, after habitually consuming their usual quantity and brand of cigarettes, their daily cigarette consumption will be reduced. It is further anticipated that puffing topography parameters will be unchanged following smoking VLN cigarettes for 6 weeks *i.e.* no smoking compensation will occur.

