2.2 Hypothesis

It is anticipated that when adult smokers switch to smoking VLN cigarettes, after habitually consuming their usual quantity and brand of cigarettes, their daily cigarette consumption will be reduced. It is further anticipated that puffing topography parameters will be unchanged following smoking VLN cigarettes for 6 weeks (i.e. no smoking compensation will occur).

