7.1.3 Puffing Topography

At clinic visits at the end of Weeks -1, 2 and 6, a randomly-selected subset of 18 non-menthol and 18 menthol smoker subjects will complete a puffing topography evaluation session with either their UB (Week -1) or the VLN (Weeks 2 and 6) cigarettes. These subjects will be/have been assigned to switch to smoking VLN cigarettes. These assessments will only be performed at a single clinical site (Lincoln) and will take place during the 24-hour confinement period.

During the puffing topography assessment, subjects will engage in a 1 hour ad libitum smoking session with their UB (Week -1) or the VLN (Weeks 2 and 6) cigarettes. In these sessions, subjects will smoke cigarettes with the mobile smoking puff analyzer (SPA-M; Sodim). The topography device will be monitored to ensure the device is actively recording during each session.

Topography assessments will be started at least one hour following either the subject's breakfast or lunch. The puffing topography session for each subject at Weeks 2 and 6 should be within \pm 2 hours of the time of their Week -1 session. Additional details and instructions for puffing topography procedures will be provided separately.

The following topography parameters will be assessed:

- Puff duration
- Puff volume
- Peak puff flow rate
- Average flow rate
- Inter-puff interval

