7.2 Data Summarization and Presentation of Primary Endpoints

Study product use (study product, CPD and cigarette butts) will be listed by subject and study week. CPD and cigarette butts will be summarized by study week and study product using descriptive statistics (number of observations [n], arithmetic mean [Mean], standard deviation [SD], coefficient of variation [CV%], standard error of the mean [SEM], minimum, median, and maximum). The total duration of the product use (sum of the duration of each product use) will also be summarized. The descriptive statistics will be presented for both PP and ITT populations.

Topography parameters (puff duration, puff volume, peak puff flow rate, average flow rate, and inter-puff interval) will be listed by subject and summarized by study product and time point (Week -1, 2, or 6).

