Appendix 16.2.5.2.2.3 Puff Topography (Safety Population)

Subject Number	Visit				Did Subject Smoke?	Number of Cigarettes Smoked*	Topography				
	Name	Date	Product Group	Date Collection			Puff (unit)	Duration (unit)	Puff Volume (unit)	Puff Flow Rate (unit)	Average Flow Rate (unit)
X	XXXX	DDMMYYYY	XX	DDMMYYYY	XX	XX	XX	XX	XX	XX	XX

Note: * How many cigarettes did the subject smoke during the 1 hour topography session?

VLN non-mentholated = Non-mentholated VLN cigarettes

VLN mentholated = Mentholated VLN cigarettes

UB non-mentholated = Subjects' UB non-mentholated filtered cigarettes

UB mentholated = Subjects' UB mentholated filtered cigarettes

Program: /CAXXXX/sas_prg/stsas/lis_PROGRAMNAME.sas DDMMYYYY HH:MM

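### Unchanged per-puff topography does not establish that smokers are not compensating, because puffs per cigarette and total puff volume per cigarette are not among the tested parameters

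*Protocol*

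**What the plan says.** The hypothesis in SAP 2.2 is that "puffing topography parameters will be unchanged following smoking VLN cigarettes for 6 weeks (i.e. no smoking compensation will occur". Protocol 1.3 makes the same equation.

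Protocol 2.2 lists the topography endpoints as "Puffing topography parameters (puff duration, puff volume, peak puff flow rate, average flow rate and inter-puff interval". The same five stand in the protocol synopsis, Protocol 5.12.5, and SAP 2.4, 7.1.3 and 7.2. SAP 7.3 compares them at Weeks 2 and 6 with Week -1 by paired t-test. Number of puffs, puffs per cigarette and total puff volume are not named as endpoints, analysis variables, tables or listing columns.

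In the measurement session, "subjects will engage in a 1 hour ad libitum smoking session with their UB (Week -1) or the VLN (Weeks 2 and 6) cigarettes", so a subject may smoke several cigarettes. Neither document says how puffs are aggregated to a cigarette or to a session. The listing in SAP Appendix 16.2.5.2.2.3 carries the answer to "How many cigarettes did the subject smoke during the 1 hour topography session", but nothing in the plan uses that count as a denominator.

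SAP 7.2 adds, for product use, "The total duration of the product use (sum of the duration of each product use) will also be summarized". This is descriptive, its data source is not given, and the SAP's list of product-use tables has no table for it.

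**The concern.** Compensation means drawing more smoke from each cigarette to make up for less nicotine. The smoke drawn from a cigarette has two factors: how many puffs are taken and how large they are. Four of the tested parameters describe a puff (duration, volume, peak flow, average flow) and the fifth describes the gap between puffs. The number of puffs is missing, so the product of the two factors is missing too.

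At stake is what the report may say if cigarettes per day (CPD) fall and the five parameters do not move. The hypothesis invites the reading that subjects smoked fewer cigarettes and drew no more from each. The second half does not follow from the five parameters. Without volume per cigarette, CPD and topography also cannot be combined into smoke drawn per day. SAP 5.1 plans topline reports built on the PK and topography outputs, so the topography result may be read without the biomarkers beside it.

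**Working it through.** **The plan's own figure.** Protocol 6.1.2 and SAP 4.2 give 12 subjects per VLN group for a two-tailed paired t-test at alpha 0.05 and 80% power. No difference or SD is stated, so 12 cannot be reproduced. Inverted with the noncentral t, it needs a standardised paired difference of 0.89 (normal approximation: (1.960 + 0.842)/√12 = 0.81). This neither supports nor contradicts the point. It matters only for the power of any added variable.

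**Identities.** For one cigarette with N puffs, mean puff volume v, mean puff duration d and inter-puff interval IPI:

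- volume drawn V = N × v
- smoking time T = N × d + (N − 1) × IPI

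Flow rates are properties of a puff and do not depend on N. If v, d, the flows and IPI are fixed, N can rise with T while all five parameters stay the same.

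**Illustration per cigarette.** Assumed values, not in the documents: N = 10, v = 50 mL, d = 1.8 s, IPI = 25 s. Then V = 500 mL and T = 10 × 1.8 + 9 × 25 = 243 s.

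Case A: extra puffs by smoking longer at the same pace. Case B: the same extra puffs within the original 243 s, so IPI = (243 − N × 1.8)/(N − 1).

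| Puffs | Volume, A and B | Time, A | Change in the five, A | IPI, B |
|---|---|---|---|---|
| 11 (+10%) | 550 mL | 270 s (+11%) | 0 | 22.3 s (−10.7%) |
| 12 (+20%) | 600 mL | 297 s (+22%) | 0 | 20.1 s (−19.5%) |
| 13 (+30%) | 650 mL | 323 s (+33%) | 0 | 18.3 s (−26.8%) |
| 15 (+50%) | 750 mL | 377 s (+55%) | 0 | 15.4 s (−38.3%) |

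In case A no sample size helps, because the expected change in every tested parameter is zero. In case B one endpoint carries the signal. The documents give no SD for IPI. If the SD of the paired difference is assumed to be 30%, 45% or 60% of baseline IPI, the power to detect the 19.5% fall is:

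| n | SD 30% | SD 45% | SD 60% |
|---|---|---|---|
| 12 (per group, sample-size section) | 0.54 | 0.28 | 0.18 |
| 18 (per group, measured subset) | 0.74 | 0.41 | 0.25 |
| 36 (both VLN groups) | 0.97 | 0.71 | 0.47 |

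**Illustration per day.** The 3 CPD fall is the plan's (Protocol 6.1.1, SAP 4.1). A rise from 10 to 12 puffs per cigarette at constant puff volume is assumed. Baseline CPD is varied upward from the inclusion minimum of 10.

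| Baseline CPD | Puffs per day before | Puffs per day after | Change | Puffs per cigarette to break even |
|---|---|---|---|---|
| 10 | 10 × 10 = 100 | 7 × 12 = 84 | −16% | 100/7 = 14.3 |
| 15 | 15 × 10 = 150 | 12 × 12 = 144 | −4% | 150/12 = 12.5 |
| 20 | 20 × 10 = 200 | 17 × 12 = 204 | +2% | 200/17 = 11.8 |
| 30 | 30 × 10 = 300 | 27 × 12 = 324 | +8% | 300/27 = 11.1 |

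The sign depends on the inputs. With 11 rather than 12 puffs at 20 CPD, the change is 17 × 11 = 187 against 200, or −6.5%.

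**The case against.** The plan is not blind to smoke exposure. At the same visits it measures 24-hour 3-HPMA, S-PMA and 1-OHP excretion and blood COHb. SAP 8.4 tests them against baseline and compares them with the groups that keep their usual brand. They are taken in all subjects, not only the 36 in the topography subset. If daily smoke volume did not fall, they could show it. This stands, but as indirect evidence: they serve a secondary objective, also move with CPD and with the change of product, and are not tied to the compensation hypothesis.

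The duration summary in SAP 7.2 is what would move in case A, and inter-puff interval would move in case B. Both are fair. The duration summary is untested and has no listed table. Complete insensitivity needs longer smoking at an unchanged pace, and nothing in the documents shows that this is the likely pattern.

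A reader might go further and infer that the trial will report an absence of compensation when subjects draw as much smoke as before, or that half of the primary objective is lost. The documents do not support either. The primary objective is to characterise CPD and topography. Compensation appears only as something anticipated in the hypothesis, and no decision rule turns the five tests into a claim. Nor does the daily illustration show that smoke drawn would rise; it falls at baselines of 10 and 15 CPD.

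Finally, puff volume is never defined as per puff. That is its ordinary meaning beside puff duration and flow rates. If a cumulative volume was intended, the plan has to say so.

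**Conclusion.** The point holds as a limit on inference. Unchanged values of the five parameters do not show that smoke drawn per cigarette is unchanged, so they cannot alone carry the statement of no compensation in Protocol 1.3 and SAP 2.2. For extra puffs taken at the same size and spacing, the insensitivity is exact: in the illustration 20% more puffs is 20% more volume, with zero change in every tested parameter. For extra puffs in the same smoking time, inter-puff interval responds, with power that depends on an unstated SD.

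At day level, a CPD fall with unchanged per-puff values may or may not mean less smoke drawn: −16% to +8% in puffs over baselines of 10 to 30 CPD, given the assumed 10 to 12 puffs per cigarette. These figures illustrate the mechanism and do not predict the result. The conclusion rests on the per-puff reading of puff volume. The five parameters remain useful for describing how smoking changes.

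**What to change.** Add puffs per cigarette and total puff volume, per cigarette and per 1-hour session, to the topography parameters in Protocol 2.2 and 5.12.5 and in SAP 2.4, 7.1.3, 7.2 and 7.3. Derive them from the existing analyser recordings, with the session cigarette count already listed as the denominator, and analyse them by the same paired test. State whether puff volume is per puff and how puffs are aggregated over a session with several cigarettes.

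Rest any statement on compensation on these variables together with the five existing parameters and the exposure biomarkers. Total volume need not be the sole deciding parameter. If the sponsor prefers not to add them, remove the clause in Protocol 1.3 and SAP 2.2 that equates unchanged topography with no compensation.

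The cost is a few more rows and tests and an amendment to the endpoint list, since Protocol 6 requires major changes to primary endpoints to be reflected in one. No new subject procedure should be needed: inter-puff interval already requires separately timed puffs, so a puff count should be recoverable. The documents do not describe the device output, so the sponsor should confirm the export. Power for the added variables cannot be stated because no SD is given. At 80% power, two-sided 0.05, the detectable standardised paired difference would be 0.70 at n = 18 and 0.48 at n = 36.

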3. SUBJECT SELECTION

3.1 Inclusion Criteria

Potential subjects must fulfill all of the following inclusion criteria to be eligible for participation in the study.

1. Is a healthy adult male or female adult smoker, 26 to 65 years of age, inclusive, at Screening.
2. Has been a smoker for at least 5 years prior to Screening. Brief periods of non-smoking (e.g., up to 7 consecutive days due to illness, trying to quit, participation in a study where smoking was prohibited) during that time will be permitted at the discretion of the Investigator.
3. Reports smoking an average of 10 or more manufactured combustible cigarettes per day at Screening.
4. Usual brand (UB) of cigarette is a filtered king size cigarette (with an approximate length of 84 mm (\pm 3 mm)).
5. Has a positive urine cotinine (\geq 500 ng/ml) at Screening.
6. Has an exhaled CO $>$ 10 ppm at Screening.
7. If female, has a negative serum pregnancy test at Screening.
8. A female subject of childbearing potential must have been using one of the following forms of contraception and agree to continue using it through completion of the study:
 - hormonal (e.g., oral, vaginal ring, transdermal patch, implant, or injection) consistently for at least 3 months prior to Screening;
 - double barrier method (e.g., condom with spermicide, diaphragm with spermicide) consistently for at least 14 days prior to Screening;
 - intrauterine device for at least 3 months prior to Screening;
 - Essure[®] or similar nonsurgical sterilization procedure at least 6 months prior to Screening

- a partner who has been vasectomized for at least 6 months prior to Screening;
 - abstinence beginning at least 14 days prior to Screening and through the End of Study.
9. A female subject of non-childbearing potential must have undergone one of the following sterilization procedures at least 6 months prior to Screening:
- hysteroscopic sterilization;
 - bilateral tubal ligation or bilateral salpingectomy;
 - hysterectomy;
 - bilateral oophorectomy;
- Or be postmenopausal with amenorrhea for at least 1 year prior to Day 1 and follicle-stimulating hormone (FSH) levels consistent with postmenopausal status.
10. Willing to comply with the requirements of the study, including a willingness to use the test products.
11. Voluntary consent to participate in this study documented on the signed informed consent form (ICF).
12. Subject is not planning to leave the area during the course of the study.

3.2 Exclusion Criteria

Subjects may be excluded from the study if there is evidence of any of the following criteria at Screening, start of Week -1 (first clinic visit), or during the study as noted, in the opinion of the Investigator.

1. History or presence of clinically significant gastrointestinal, renal, hepatic, neurologic, hematologic, endocrine, oncologic, urologic, pulmonary (especially bronchospastic diseases and asthma), immunologic, psychiatric, or cardiovascular disease, or any other condition that, in the opinion of the Investigator, would jeopardize the safety of the subject or impact the validity of the study results.
2. Clinically significant abnormal findings on the physical examination, medical history, ECG, or clinical laboratory results, in the opinion of the Investigator.
3. Positive test for human immunodeficiency virus (HIV), hepatitis B surface antigen (HBsAg), or hepatitis C virus (HCV).
4. An acute illness (e.g., upper respiratory infection, viral infection) requiring treatment with prescription medication(s) within 14 days prior to Screening or first clinic visit.
5. Fever (>100.5°F) at Screening or first clinic visit.
6. Body mass index (BMI) greater than 40.0 kg/m² or less than 18.0 kg/m² at Screening.
7. History of drug or alcohol abuse or has used medical/recreational marijuana within 12 months of Screening.
8. Diabetes mellitus that is not controlled by diet/exercise alone, in the opinion of the Investigator.
9. Seated heart rate is lower than 40 bpm or higher than 99 bpm at Screening, unless deemed not clinically significant by the PI.

10. Seated systolic blood pressure <90 mmHg or >150 mmHg, diastolic blood pressure <40 mmHg or >95 mmHg at Screening, unless deemed not clinically significant by the PI.
11. Positive urine screen for drugs of abuse or alcohol at Screening or at the first clinic visit.
12. Female subjects who are pregnant, lactating, or intend to become pregnant from Screening through the End of Study.
13. Use of medications known to interact with cytochrome p450 2A6 (including, but not limited to, amiodarone, desipramine, isoniazid, ketoconazole, miconazole, phenobarbital, rifampin, tranylcypromine, methoxsalen) within 3 months prior to Screening and throughout the study.
14. Use of inhalers to treat any medical condition within 3 months prior to Screening and throughout the study.
15. Use of nicotine-containing products other than factory manufactured cigarettes [e.g., roll-your-own cigarettes, e-vapor products, bidis, snuff, nicotine inhaler, pipe, cigar, chewing tobacco, nicotine patch, nicotine spray, nicotine lozenge, or nicotine gum] within 28 days prior to Screening.
16. Use of any prescription smoking cessation treatments, including, but not limited to, varenicline (Chantix[®]) or bupropion (Zyban[®]) within 3 months prior to Screening.
17. Self-reported puffer/non-inhaler (*i.e.*, a smoker who draws smoke from the cigarette into the mouth and throat but does not inhale).
18. Planning to quit smoking during the study period or postponing a quit attempt in order to participate in the study.
19. Plasma donation within 7 days prior to Screening or at any time during the study.
20. Donation of blood or blood products (with the exception of plasma as noted above), had significant blood loss, or received whole blood or a blood product transfusion within 56 days prior to Screening.
21. Participation in a previous clinical study for an investigational drug, device, biologic, or tobacco product within 30 days prior to Screening.
22. Subject or a first-degree relative (*i.e.*, parent, sibling, child) is a current or former employee of the tobacco industry or a named party or class representative in litigation with the tobacco industry.
23. Subject or a first-degree relative (*i.e.*, parent, sibling, child) is a current employee of the clinic sites.

3.3 Study Restrictions

3.3.1 Concomitant Medications

Except for those medications noted in the exclusion criteria (See [Section 3.2](#)), stable doses (*i.e.*, no dosage adjustments within approximately 30 days prior to Check-in) of prescription or over-the-counter medications required to treat an Investigator-approved disease or condition (e.g., hypertension) are permitted at the discretion of the Investigator. Hormonal contraceptives (e.g., oral, vaginal ring, transdermal patch, implant, injection) and hormonal replacement therapy are permitted. Occasional use of over-the-counter analgesics (e.g., acetaminophen, ibuprofen), antihistamines, nasal decongestants, and

dietary supplements are permitted. Exceptions may be permitted at the discretion of the Investigator in consultation with the Sponsor, providing the medication in question would have no impact on the study. Any exceptions will be documented.

All concomitant medications (and reasons for their use) taken by subjects during the study will be recorded and listed.

3.3.2 Foods and Beverages

Consumption of foods and beverages containing the following substances should not be consumed as indicated below.

- Xanthines/caffeine: throughout each clinic visit, apart from one approximately 250ml caffeinated beverage with each meal.
- Alcohol: 48 hours prior to and throughout each clinic visit.

Exceptions may be permitted at the discretion of the Investigator.

3.3.3 Activity

Subjects will be instructed to refrain from strenuous physical activity outside of their usual routine for the whole study period between Screening and the end of Week 6.

3.4 Subject Numbering

Subjects will be assigned a unique screening number. Upon enrollment into the study, a definitive subject number will be assigned. Replacement subjects may be used at the discretion of the Sponsor.

3.5 Subject Early Discontinuation or Withdrawal

Subjects will be advised that they are free to withdraw from the study at any time. In addition, subject participation in this trial may be discontinued for any of the following reasons.

- Adverse event
- Lost to follow-up
- Non-compliance with study procedures
- Protocol violation
- Pregnancy for female subjects
- Study terminated by Sponsor, US Food and Drug Administration (FDA), or other regulatory authorities
- Withdrawal of consent
- Investigator's discretion, including a severe laboratory abnormality or other medical condition that indicates to the Investigator that continued participation is not in the best interest of the subject

Subject's e-diary completion rates will be checked at each study visit. If the percentage of days on which the e-diary was completed is below 70%, subjects may be withdrawn from the study.

Other protocol deviations/violations should not lead to subject withdrawal unless they indicate a significant risk to the subject's safety or jeopardize the scientific integrity of the study.

If premature withdrawal from the study occurs for any reason, the Investigator must determine the primary reason and record this information in the case report form (CRF). Additionally, subjects withdrawing after study product use will undergo all end-of-study safety procedures as feasible and as deemed necessary by the Investigator.

A subject withdrawn from the study due to any AE or clinically significant abnormal laboratory test values will be evaluated by the Investigator or other monitoring physician and will be treated and/or followed up until the symptoms or values return to normal or acceptable levels or until lost to follow-up, as appropriate in the opinion of the Investigator.

Subjects withdrawing or removed from this study cannot re-enter.

